#### Exclusion Criteria

Patients who meet any of the following criteria will be excluded from study entry:

- Secondary progressive multiple sclerosis (SPMS) or history of primary progressive or progressive relapsing MS
- Inability to complete an MRI (contraindications for MRI include but are not restricted to pacemaker, cochlear implants, presence of foreign substances in the eye, intracranial vascular clips, surgery within 6 weeks of entry into the study, coronary stent implanted within 8 weeks prior to the time of the intended MRI, inability to tolerate Gadolinium-based contrast agents etc.)
- Known presence of other neurological disorders, including but not limited to, the following:
  - History of ischemic cerebrovascular disorders (e.g., stroke, transient ischemic attack) or ischemia of the spinal cord
  - History or known presence of CNS or spinal cord tumor (e.g., meningioma, glioma)
  - History or known presence of potential metabolic causes of myelopathy (e.g., untreated vitamin B12 deficiency)
  - History or known presence of infectious causes of myelopathy (e.g., syphilis, Lyme disease, human T-lymphotropic virus 1 (HTLV-1), herpes zoster myelopathy)
  - History of genetically inherited progressive CNS degenerative disorder (e.g., hereditary paraparesis; MELAS [mitochondrial myopathy, encephalopathy, lactic acidosis, stroke] syndrome)
  - Neuromyelitis optica
  - History or known presence of systemic autoimmune disorders potentially causing progressive neurologic disease (e.g., lupus, anti-phospholipid antibody syndrome, Sjogren's syndrome, Behçet's disease)
  - History or known presence of sarcoidosis

- History of severe, clinically significant brain or spinal cord trauma (e.g., cerebral contusion, spinal cord compression)

#### Exclusions Related to General Health

- Pregnancy or lactation
- Any concomitant disease that may require chronic treatment with systemic corticosteroids or immunosuppressants during the course of the study
- History or currently active primary or secondary immunodeficiency
- Lack of peripheral venous access
- History of severe allergic or anaphylactic reactions to humanized or murine monoclonal antibodies
- Significant or uncontrolled somatic disease or any other significant disease that may preclude patient from participating in the study
- Congestive heart failure (New York Heart Association [NYHA] III or IV functional severity)
- Known active bacterial, viral, fungal, mycobacterial infection or other infection, excluding fungal infection of nail beds  
Note: Active infections should be treated and effectively controlled before possible inclusion in the study
- History of major opportunistic infections (i.e. cryptococcosis, Pneumocystis pneumonia, progressive multifocal leukoencephalopathy [PML])
- History or known presence of recurrent or chronic infection (e.g., hepatitis B or C, human immunodeficiency virus [HIV], syphilis, tuberculosis [TB])
- History of malignancy, including solid tumors and hematological malignancies, except basal cell carcinoma, in situ squamous cell carcinoma of the skin, and in situ carcinoma of the cervix of the uterus that have been previously completely excised with documented, clear margins
- History of alcohol or drug abuse within 24 weeks prior to baseline
- History or laboratory evidence of coagulation disorders

#### Exclusions Related to Medications\*

- Receipt of a live vaccine or attenuated live vaccine within 6 weeks prior to the baseline visit. In rare cases when patient requires vaccination with a live vaccine, the screening period may be extended but cannot exceed 8 weeks
- Treatment with any investigational agent within 24 weeks of screening (Visit 1) or five half-lives of the investigational drug (whichever is longer) or treatment with any experimental procedures for MS (e.g., treatment for chronic cerebrospinal venous insufficiency)
- Contraindications to or intolerance of oral or IV corticosteroids, according to the country label, including:
  - a) Psychosis not yet controlled by a treatment;
  - b) Hypersensitivity to any of the constituents
- Previous treatment with B-cell targeted therapies (i.e., rituximab, ocrelizumab, atacicept, belimumab, or ofatumumab)
- Systemic corticosteroid therapy within 4 weeks prior to screening
- Any previous treatment with alemtuzumab (Campath/Mabcampath/Lemtrada), cladribine, mitoxantrone, daclizumab, laquinimod, total body irradiation, or bone marrow transplantation.
- Treatment with cyclophosphamide, azathioprine, mycophenolate mofetil, cyclosporine or methotrexate
- Previous treatment with natalizumab unless natalizumab was discontinued because of persistent anti-natalizumab antibodies
- Treatment with IV immunoglobulin (Ig) within 12 weeks prior to baseline

- Any previous treatment with an investigational MS DMT not yet approved at time of screening.
- History of recurrent aspiration pneumonia requiring antibiotic therapy
- Patients previously treated with teriflunomide, unless an accelerated elimination procedure is implemented before screening visit

Accelerated elimination procedure after stopping treatment with teriflunomide:

- cholestyramine 8g is administered 3 times daily for a period of 11 days, or cholestyramine 4g three times a day can be used, if cholestyramine 8g three times a day is not well tolerated,
- alternatively, 50g of activated powdered charcoal is administered every 12 hours for a period of 11 days

In cases where no pregnancy is expected teriflunomide plasma concentrations of 0.03-0.04 mg/ml are accepted to include the patient in study.

- Previous treatment with fingolimod or dimethyl fumarate if at baseline the lymphocyte count is below lower limit of normal (LLN). The provisions for stopping therapy as described in the respective SmPCs should be followed.
- Treatment with fampridine/dalfampridine (Fampyra®)/Ampyra® unless on stable dose for  $\geq 30$  days prior to screening. Wherever possible, patients should remain on stable doses throughout the 96-week treatment period.

\* Patients screened for this study should not be withdrawn from therapies for the sole purpose of meeting eligibility for the trial.

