#### Exclusions Related to Medications\*

- Receipt of a live vaccine or attenuated live vaccine within 6 weeks prior to the baseline visit.  
In rare cases when patient requires vaccination with a live vaccine, the screening period may be extended but cannot exceed 8 weeks.
- Treatment with any investigational agent within 24 weeks of screening (Visit 1) or five half-lives of the investigational drug (whichever is longer) or treatment with any experimental procedures for MS (e.g., treatment for chronic cerebrospinal venous insufficiency).

- Contraindications to or intolerance of oral or IV corticosteroids, according to the country label, including:
  - a) Psychosis not yet controlled by a treatment;
  - b) Hypersensitivity to any of the constituents.
- Previous treatment with B-cell targeted therapies (i.e., rituximab, ocrelizumab, atacicept, belimumab, or ofatumumab).
- Systemic corticosteroid therapy within 4 weeks prior to screening.
- Any previous treatment with alemtuzumab (Campath/Mabcampath/Lemtrada), cladribine, mitoxantrone, daclizumab, laquinimod, total body irradiation, or bone marrow transplantation.
- Treatment with cyclophosphamide, azathioprine, mycophenolate mofetil, cyclosporine or methotrexate.
- Previous treatment with natalizumab unless natalizumab was discontinued because of persistent anti-natalizumab antibodies.
- Treatment with IV Ig within 12 weeks prior to baseline.
- Any previous treatment with an investigational MS DMT not yet approved at time of screening.
- History of recurrent aspiration pneumonia requiring antibiotic therapy.
- Patients previously treated with teriflunomide, unless an accelerated elimination procedure is implemented before screening visit.

Accelerated elimination procedure after stopping treatment with teriflunomide:

- cholestyramine 8g is administered 3 times daily for a period of 11 days, or cholestyramine 4g three times a day can be used, if cholestyramine 8g three times a day is not well tolerated,
- alternatively, 50g of activated powdered charcoal is administered every 12 hours for a period of 11 days.
- Previous treatment with fingolimod or dimethyl fumarate if at baseline the lymphocyte count is below lower limit of normal (LLN). The provisions for stopping therapy as described in the respective SmPCs should be followed.

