## 5.2 Pharmacokinetic properties

### Absorption

Median time to reach maximum plasma concentrations occurs between 1 to 4 hours post-dose following repeated oral administration of teriflunomide, with high bioavailability (approximately 100%).

Food does not have a clinically relevant effect on teriflunomide pharmacokinetics.

From the mean predicted pharmacokinetic parameters calculated from the population pharmacokinetic (PopPK) analysis using data from healthy volunteers and MS patients, there is a slow approach to steady-state concentration (i.e., approximately 100 days (3.5 months) to attain 95% of steady-state concentrations) and the estimated AUC accumulation ratio is approximately 34-fold.

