#### Distribution

Teriflunomide is extensively bound to plasma protein (>99%), probably albumin and is mainly distributed in plasma. The volume of distribution is 11 l after a single intravenous (IV) administration. However, this is most likely an underestimation since extensive organ distribution was observed in rats.

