#### Elimination

Teriflunomide is excreted in the gastrointestinal tract mainly through the bile as unchanged medicinal product and most likely by direct secretion. Teriflunomide is a substrate of the efflux transporter BCRP, which could be involved in direct secretion. Over 21 days, 60.1% of the administered dose is excreted via feces (37.5%) and urine (22.6%). After the rapid elimination procedure with cholestyramine, an additional 23.1% was recovered (mostly in feces). Based on individual prediction of pharmacokinetic parameters using the PopPK model of teriflunomide in healthy volunteers and MS patients, median  $t_{1/2z}$  was approximately 19 days after repeated doses of 14 mg. After a single IV administration, the total body clearance of teriflunomide is 30.5 ml/h.

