#### *Accelerated Elimination Procedure: Cholestyramine and activated charcoal*

The elimination of teriflunomide from the circulation can be accelerated by administration of cholestyramine or activated charcoal, presumably by interrupting the reabsorption processes at the intestinal level.

Teriflunomide concentrations measured during an 11-day procedure to accelerate teriflunomide elimination with either 8 g cholestyramine three times a day, 4 g cholestyramine three times a day or 50 g activated charcoal twice a day following cessation of teriflunomide treatment have shown that these regimens were effective in accelerating teriflunomide elimination, leading to more than 98% decrease in teriflunomide plasma concentrations, with cholestyramine being faster than charcoal. Following discontinuation of teriflunomide and the administration of cholestyramine 8 g three times a day, the plasma concentration of teriflunomide is reduced 52% at the end of day 1, 91% at the end of day 3, 99.2% at the end of day 7, and 99.9% at the completion of day 11. The choice between the 3 elimination procedures should depend on the patient's tolerability. If cholestyramine 8 g three times a day is not well-tolerated, cholestyramine 4 g three times a day can be used. Alternatively, activated charcoal may also be used (the 11 days do not need to be consecutive unless there is a need to lower teriflunomide plasma concentration rapidly).

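### The synopsis accepts teriflunomide at 0.03–0.04 mg/ml, roughly full-dose exposure, and Section 4.1.2 carries no such sentence

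*Protocol*

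**What the plan says.** Three places state the teriflunomide criterion: the Protocol Synopsis (Exclusions Related to Medications), Protocol Section 4.1.2, and the synopsis reproduced in SAP Appendix 1. All three exclude "Patients previously treated with teriflunomide, unless an accelerated elimination procedure is implemented before screening visit", and all three then list the same cholestyramine or charcoal regimens over 11 days.

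The synopsis and its SAP copy then add one more sentence: "In cases where no pregnancy is expected teriflunomide plasma concentrations of 0.03-0.04 mg/ml are accepted to include the patient in study". Section 4.1.2 does not have it.

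Protocol Appendix 8 reproduces the teriflunomide product information. It expresses its own concentration threshold in mg/l (0.02 mg/l). For the 11-day procedure it reports regimens "leading to more than 98% decrease in teriflunomide plasma concentrations". For cholestyramine 8 g three times daily it says that "the plasma concentration of teriflunomide is reduced 52% at the end of day 1", and it gives later falls of "99.2% at the end of day 7, and 99.9% at the completion of day 11".

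Protocol Section 4.5.8 (laboratory samples) and Appendix 1 (schedule of assessments) contain no teriflunomide assay. Section 3.1.2 sends investigators to the local label, and to Appendix 8, for washout of earlier treatments.

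**The concern.** There are two problems. First, a site working from the synopsis and a site working from Section 4.1.2 apply different criteria. Second, the printed figure looks far too high to serve as evidence that teriflunomide has been cleared.

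The sentence does not say whether the concentration is a further condition after the procedure or an alternative to it. If it is further, it excludes almost nobody. If it is an alternative, it admits patients at on-treatment exposure. It also gives no sampling time.

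Two things are at stake. One is overlap of immune effects at the start of ocrelizumab, which Protocol Section 4.4.2 and the switching text in Appendix 8 both caution about. The other is how a patient is classified. SAP Section 4.1.3 removes patients from the per-protocol population for exclusions related to previous treatments, SAP Section 4.2 lists eligibility violations, and SAP Section 4.4.5 names teriflunomide as a last-treatment subgroup. Which version governs can decide whether a switcher counts as a violator.

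**Working it through.** The documents give no derivation of 0.03–0.04 mg/ml, so there is no calculation to reproduce. The check compares it with levels that follow from Appendix 8.

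**Unit conversion.** 0.03 to 0.04 mg/ml × 1,000 = 30 to 40 mg/l.

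**Inputs** (Appendix 8, teriflunomide SmPC Sections 4.2 and 5.2): dose 14 mg daily; bioavailability about 100%; "the total body clearance of teriflunomide is 30.5 ml/h"; median half-life about 19 days; volume of distribution 11 l after a single intravenous dose, of which the text says "this is most likely an underestimation"; and "the estimated AUC accumulation ratio is approximately 34-fold".

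**Average steady state by three routes**

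| Route | Calculation | Steady state | 30–40 mg/l ÷ steady state |
|---|---|---|---|
| (a) dose ÷ clearance | 14 ÷ (0.0305 × 24) | 19.1 mg/l | 1.57–2.09 |
| (b) dose ÷ (k × V), k = ln 2 ÷ 19 | 14 ÷ (0.0365 × 11) | 34.9 mg/l | 0.86–1.15 |
| (c) dose ÷ V × accumulation | 14 ÷ 11 × 34 | 43.3 mg/l | 0.69–0.92 |

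Route (c) scales an initial level. Using the average over the first day instead gives 42.6 mg/l, which changes nothing. Across routes the accepted range is 0.7 to 2.1 times full-dose exposure.

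**Levels left during and after the procedure (mg/l)**

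| Fall | From 19.1 | From 34.9 | From 43.3 |
|---|---|---|---|
| 52% (day 1, cholestyramine 8 g) | 9.2 | 16.7 | 20.8 |
| 98% (Appendix 8 says more than this, all regimens) | 0.38 | 0.70 | 0.87 |
| 99.2% (day 7, cholestyramine 8 g) | 0.15 | 0.28 | 0.35 |
| 99.9% (day 11, cholestyramine 8 g) | 0.019 | 0.035 | 0.043 |

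After one day of the 8 g regimen every route is already below 30 mg/l. Against the 98% residual the accepted range is 30 ÷ 0.865 = 35 to 40 ÷ 0.383 = 105 times higher.

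**With no procedure.** A patient at steady state is already at or below 40 mg/l on routes (a) and (b), and gets there within about 2 days of stopping on route (c). For 30 mg/l the wait is 0 days on (a), 4–5 days on (b) and 10–12 days on (c), using half-lives of 19 to 23.2 days. The longer half-life is the one implied by 34-fold accumulation.

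**Other reference points.** 30 ÷ 0.02 = 1,500 and 40 ÷ 0.02 = 2,000 times the Appendix 8 threshold. A five-half-life washout divides by 32 and leaves 19.1 ÷ 32 = 0.60 to 43.3 ÷ 32 = 1.35 mg/l.

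**If the unit were mg/l.** The range would be 0.03 ÷ 0.02 = 1.5 to 0.04 ÷ 0.02 = 2 times that threshold, and it would lie within the 0.019–0.043 mg/l spread of the day-11 residuals.

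**The case against.** **The procedure is mandatory in every version.** The sentence comes after the procedure's steps and does not claim to replace them. Read that way it is inert, and no patient enters at treatment-level exposure. This is the most natural reading, and it limits the likely harm. It does not rescue the sentence, which would then be a limit that excludes almost nobody and appears in only some copies of the criterion.

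**The unit may be a lost Greek letter.** Micrograms per ml would equal mg/l, and the pregnancy-test footnote in the schedule shows a Latin b where β is meant. But µ is read correctly elsewhere, including the laboratory exclusions in the same SAP synopsis. The cause stays open. The support from the day-11 residuals is also modest: only route (b), at 0.035 mg/l, falls inside 0.03–0.04, and the 99.9% figure applies to one regimen.

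**The pharmacokinetic inputs do not fit one model.** Clearance of 30.5 ml/h with 11 l implies a half-life of ln 2 × 11 ÷ 0.732 = 10.4 days, against the stated 19. Routes (b) and (c) both use that volume. This is right, so steady state is known only as an order of magnitude. Route (a) does not use the volume, and it puts the accepted range further above steady state, so the direction holds.

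**The 0.02 mg/l benchmark is mainly about pregnancy and contraception**, while the sentence is confined to cases where no pregnancy is expected. That stands. The 1,500–2,000 ratio is context; the comparisons with steady state and with the post-procedure residual carry the argument.

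**No endpoint, estimate or sample size changes.** That is correct, and the number of teriflunomide switchers is not given.

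**Conclusion.** The concern holds. The mismatch between the synopsis (with its SAP copy) and Section 4.1.2 is certain from the text and survives any reading of the unit. As written, the concentration is about full-dose exposure (0.7 to 2.1 times derived steady state) and at least about 35 times what a 98% fall would leave, so it cannot show that the elimination procedure was done.

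This rests on four assumptions: mg/ml is the intended unit; the range is read as an upper limit, although the sentence gives only a band; steady state is derived from Appendix 8, not printed there; and all levels are averages, because between-patient variability is not taken into account. The effect on trial results cannot be quantified. The point should be fixed because it bears on patient safety and on who counts as an eligibility violator.

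**What to change.** Reconcile the Protocol Synopsis, SAP Appendix 1, Protocol Section 4.1.2 and Appendix 8, and check consistency with the washout reference in Section 3.1.2. State one teriflunomide eligibility rule, identically in each place, with:

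- one threshold, in one unit verified against the source;
- whether it applies in addition to the elimination procedure or instead of it;
- when the level is measured, with the assay added to Section 4.5.8 and Appendix 1 if it is required.

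If Section 4.1.2 is meant to govern, remove the sentence from both synopses. The value and the rule are for the sponsor's clinical team; none is proposed here.

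The cost is a wording correction by amendment or clarification letter. If enrolment has closed, issue the clarification and check in the eligibility records which version was applied to each enrolled teriflunomide switcher, before the per-protocol population and the violation listing are fixed.

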#### Exclusions Related to Laboratory Findings\*

- Positive serum  $\beta$  human chorionic gonadotropin (hCG) measured at screening
- Positive screening tests for hepatitis B (hepatitis B surface antigen [HBsAg] positive, or positive hepatitis B core antibody [total HBcAb] confirmed by a positive viral DNA polymerase chain reaction [PCR]) or hepatitis C (HepCAb)
- Lymphocyte count below LLN
- CD4 count  $< 250/\mu\text{L}$ .
- Aspartate aminotransferase (AST)/ serum glutamic oxaloacetic transaminase (SGOT) or alanine aminotransferase (ALT) /serum glutamic pyruvic transaminase (SGPT)  $\geq 3.0 \times$  the upper limit of normal (ULN)
- Platelet count  $< 100,000/\mu\text{L}$  ( $< 100 \times 10^9/\text{L}$ )
- Absolute neutrophil count  $< 1.0 \times 10^3/\mu\text{L}$

\*Re-testing before baseline: any abnormal screening laboratory value that is clinically relevant should be retested in order to rule out any progressive or uncontrolled underlying condition. The last value before baseline visit must meet study criteria.

Please note: based on local Ethics Committees or National Competent Authority requirements, additional diagnostic testing may be required for selected patients or selected centers to exclude tuberculosis, Lyme disease, HTLV-1 associated myelopathy (HAM), acquire immunodeficiency syndrome (AIDS), hereditary disorders, connective tissue disorders, or sarcoidosis. Other specific diagnostic tests may be requested when deemed necessary by the Investigator.

#### **End of Study**

The end of the study treatment period has been defined as the date on which the last patient receiving the full study treatment reached the 96-week visit. Exception will be made for patients who have EDSS change at Week 96 and need confirmation of EDSS score after a further 24 weeks.

The end of the study is defined as the last patient last visit in the B-cell monitoring of the Follow-up Period.

At the end of the study treatment, patients will be encouraged to be included in a separate LTE study to further evaluate the efficacy and safety of their DMT treatment and this is independent of the DMT administered. This LTE will also aim to evaluate the relationship between the primary endpoint of this study and long-term outcome.

### **Length of Study**

The total length of the study, from screening of the first patient to the end of the study, is expected to be approximately 5 years. This includes an enrollment period of approximately 12 months.

### **Investigational Medicinal Products**

#### **Test Product (Investigational Drug)**

The first dose of ocrelizumab will be administered as two 300-mg IV infusions (600 mg total) in 250 mL 0.9% sodium chloride each separated by 14 days (i.e., Days 1 and 15), followed by one 600-mg IV infusion in 500 mL 0.9% sodium chloride every subsequent dose (i.e., every 24 weeks) for a maximum of 4 doses.

#### **Non-Investigational Medicinal Products**

Premedicate with 100 mg of methylprednisolone (or an equivalent), administered by slow IV infusion, to be completed approximately 30 minutes prior to each ocrelizumab infusion, and an antihistaminic drug (e.g., diphenhydramine) approximately 30 – 60 minutes before each infusion of ocrelizumab to reduce the frequency and severity of infusion-related reactions (IRRs). The addition of an antipyretic (e.g., acetaminophen/ paracetamol) may also be considered.

### **Statistical Methods**

#### **Primary Analysis**

The primary efficacy analyses will include all enrolled patients who received any dose of ocrelizumab (intent-to-treat population). The analysis will be performed after the last CDP and CDI confirmation visit. The per-protocol population, defined as all patients who had 96 weeks of treatment and who did not have any major protocol violations that are deemed to potentially affect the efficacy and safety endpoints, will be used for supportive efficacy analyses of the primary endpoint.

The evaluation of the clinical efficacy of ocrelizumab will be based upon the events in-between the baseline visit and week 96 visit. The MRI activity is evaluated from week 8 to week 96.

The proportion of patients free from protocol-defined events up to Week 96 (i.e. patients with NEDA) will be calculated and the corresponding two-sided Clopper-Pearson 95% confidence interval (CI) will be presented. Logistic regression models will be used to identify predictors of response to treatment (freedom from protocol-defined events of disease activity). Variables that will be considered are: region, line of treatment (previous DMTs), gender, and baseline EDSS. In addition, specific efficacy endpoints, such as CDP, will be compared between patients with or without evidence of disease activity up to Week 96.

Details about the missing data handling, as well as sensitivity analyses, will be specified in the statistical analysis plan.

